The Respiratory Therapist (RT) will perform the CLT on all enrolled patients. The patients will first be switched to volume assist-control (V-AC) with a respiratory rate of 10 breaths/min (to allow patient assist), constant flow of 60 l/min, and tidal volume set to match the average tidal volume currently being delivered during supportive ventilation. The RT will document the average exhaled volume over 3-5 breaths after switching to V-AC. The test will be performed by deflating the ETT balloon cuff with a 10 cc syringe, and: a) auscultation with a stethoscope to identify audible air leak around the ETT, and b) measuring the difference between the average

exhaled volume prior to cuff deflation and the average exhaled volume over 3-5 breaths after cuff deflation.

We define a “failed CLT” as the RT being unable to identify air leak during auscultation.

Patients randomized to the intervention arm will have the results of the CLT (whether failed or passed CLT) communicated to the treating physician; the treating physician will decide whether to proceed with extubation or not based on the CLT results. It is at the discretion of the treating physician to provide corticosteroids (4-5 mg of intravenous dexamethasone every six hours for up to 24 hours, with the last dose given one hour preceding extubation) and/or delay extubation by 24 hours should the patient fail the CLT²³.

In the control arm of this trial; the treating physicians and healthcare workers will be blinded to the results of CLT; therefore, the RT will proceed with extubation without delay or administering systemic steroid, regardless to the CLT results.

Patients, physicians, RCs, study investigators, adjudicators, and data analysts will be blinded to the results of CLT in the control group.

OUTCOMES

Feasibility Outcomes

Although we will report all clinical outcomes relevant for the future COMIC RCT, the primary outcomes of the COMIC Pilot Trial will be the following feasibility outcomes:

- 1) Consent Rate: a successful consent rate will be defined as 70% of SDMs or patients approached to consent, choosing to participate in the trial. This will be calculated as the overall proportion of SDMs or patients consenting out of those approached (with 95% CI). As this is a Pilot Trial, the consent rate will be reviewed monthly and if applicable, barriers to informed

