consent will be discussed and factors associated with improved consent as produced by the CCCTG Research Coordinators will be employed²¹.

2) Recruitment Rate: a successful recruitment rate will be defined as achieving enrolment of 40 patients, conventionally expressed as four patients per month over the duration of the trial. While the pilot trial is ongoing, recruitment will be reviewed weekly and the screening records will be reviewed monthly with the cases of missed eligible patients reviewed. If applicable, barriers to enrolment will be addressed to maximize recruitment. The recruitment metric will be measured and interpreted at the end of the pilot trial by calculating the mean number of recruited patients per active screening month.

3) Protocol Adherence: Successful adherence will be defined as $\geq 80\%$ of patients assigned to the intervention arm being treated as previously described. The adherence will be calculated as the proportion of patients that were assigned to the control arm being extubated after CLT being performed and the portion of people that assigned to the intervention arm who are given the prescribed steroids for a failed CLT. As this pilot trial is ongoing, we will review adherence monthly and investigate the reasons for compliance failure. All reasons for either failure to extubate after a failed CLT in the control arm will be investigated. The RC will review the Respiratory Therapists' notes, and the medication profile to determine actual compliance. All reasons for non-compliance will be recorded for both groups using distinguishing clinical reasons (eg. Palliation, death, consent withdrawal, errors).

Clinical Outcomes

The clinical outcomes are:

- 1) Postextubation stridor: defined as an audible high pitched inspiratory noise caused by turbulent airflow through the narrowed airway that is detectable with or without a stethoscope within 48 hours of extubation.
- 2) Clinically significant postextubation stridor: Defined as stridor (see definition above) that requires medical intervention such as the administration of systemic steroids, racemic epinephrine, or Heli-ox.
- 3) Reintubation: defined as reintubation within 72 hours of original extubation while in the ICU. Reasons for intubation will be recorded.
- 4) Emergency surgical airway: defined as performing urgent tracheostomy or cricothyroidotomy for a life-threatening airway obstruction.
- 5) In ICU mortality.
- 6) In hospital mortality truncated at 30 days.

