- 7) Duration of mechanical ventilation: defined as time on the ventilator after randomization in days.
- 8) ICU length of stay in days.

Clinical outcome adjudication

The RC will enter data in a web-base and send relevant clinical information to staff at the methods centre who will validate data and prepare adjudication packages for all clinical outcomes. Two independent blinded physicians will adjudicate post extubation stridor and reintubation outcomes.

Data collection and follow-up

The RC will screen the ICU Monday to Friday to avoid incurring additional weekend on-call costs. RC will collect information including the patient baseline data (e.g., demographics, illness severity, advanced life support including duration of mechanical ventilation, daily data (e.g., CLT results, postextubation stridor, rate of reintubation, steroids administered), and source documentation that will help with adjudication of outcomes. RC will review patients daily in the ICU where the trial data including mortality, length of stay, and length of mechanical ventilation will be gathered. Once patients are discharged from the ICU they will no longer be followed daily, but incidence of in hospital mortality will be assessed at time of hospital discharge. Mortality, duration of ventilation, and ICU stay outcomes will be censored at 60 days.

Duration of the COMIC Pilot Trial

We anticipate that 10 months will be required to recruit 40 patients. A subsequent three months will be needed to validate the data, adjudicate the outcomes, analyze, interpret and present results. The total duration of the Pilot Trial may take up to 13 months to complete.

Analysis of the COMIC Pilot Trial

Calculation of consent and recruitment feasibility outcomes for the COMIC Pilot Trial will not require analysis by group, however compliance rates will have to be assessed for each group. Therefore, clinical outcomes will be analyzed as means or proportions in each arm. In addition, given the small sample size and short duration, we will not conduct any subgroup or interim analyses. An independent data safety and monitoring board will be created for the large COMIC RCT.

The proportion of patient in the two groups with the primary and secondary outcomes will be

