analyzed using the Mantel-Haenszel χ^2 test or Fisher exact test. A t-test will be used for continuous outcomes and a statistical significance will be set at alpha=0.05. We will develop a full statistical analysis plan adherent to the intention to treat principle and some subgroup analysis (e.g., size of endotracheal tube).

DISCUSSION

Extubation can be a precarious step for patients admitted to the ICU. Therefore, critical care physicians undertake the utmost cautions prior to extubating patients. Moderate quality evidence supports the use of a spontaneous breathing trials with inspiration pressure augmentation as a method to predict a patient's capacity to breath upon liberation from the ventilator²⁰. CLT is the most commonly used test to detect LE in mechanically ventilated patients. However, the diagnostic accuracy and impact on clinical outcomes in average risk patients are unclear. Therefore, recent guidelines issued a weak recommendation to perform CLT prior to extubating high risk patients (i.e. traumatic intubation, a large endotracheal tube, or reintubated after an unplanned extubation)¹⁷. Patients who fail a CLT are often treated with high dose systemic corticosteroids and extubation may be delayed, both outcomes are likely not desirable by most patients.

To our knowledge, only observational studies showed that in subsets of patients; a CLT may help identify patients at higher risk of airway obstruction. We therefore, have presented a protocol for a pilot RCT to determine the feasibility of examining the effect of using CLT on postextubation complications, versus not using the test. Physician and public acceptance of performing such a

protocol is uncertain and it is integral that the recruitment rate, consent rate, and adherence rate are examined before a large scale RCT is pursued.

In conclusion, this protocol describe in detail the design and methodology of COMIC Pilot Trial. We believe that the results of this trial will help inform the design and the conduct of a large RCT examining the effect of bedside CLT on postextubation events in average risk mechanically ventilated patients.

References

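### Stridor and reintubation can occur only after extubation, which depends on the CLT result in one arm only, so an intervention patient who is never extubated counts as a non-event

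*Protocol*

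**What the plan says.** **Outcomes (Protocol, Clinical Outcomes, items 1 to 3).** Stridor is a noise from a "narrowed airway that is detectable with or without a stethoscope within 48 hours of extubation". Clinically significant stridor takes over that definition. Reintubation is "defined as reintubation within 72 hours of original extubation while in the ICU".

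**Intervention arm (Protocol, Intervention).** Once the result is known, "the treating physician will decide whether to proceed with extubation or not based on the CLT results". The physician may give corticosteroids "and/or delay extubation by 24 hours should the patient fail the CLT".

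**Control arm (same section).** The result is withheld and "the RT will proceed with extubation without delay or administering systemic steroid, regardless to the CLT results".

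**Analysis (Protocol, Analysis of the COMIC Pilot Trial).** The section says that "clinical outcomes will be analyzed as means or proportions in each arm". The arms are then compared by a Mantel-Haenszel or Fisher test, in a sentence that begins "The proportion of patient in the two groups with the primary and secondary outcomes will be". It promises a "full statistical analysis plan adherent to the intention to treat principle".

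The protocol does not say how to count a randomized patient who is never extubated. Duration of mechanical ventilation, by contrast, runs from randomization.

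**The concern.** Being at risk of stridor or reintubation requires extubation. In control, extubation follows whatever the test shows. In the intervention arm it depends on the test result, and the option not to extubate has no stated time limit. An intervention patient with a failed CLT might therefore be held, worsen, and die on the ventilator or receive a planned tracheostomy. That patient can have no stridor and no reintubation. A planned tracheostomy is not an emergency surgical airway either. A similar control patient is extubated and exposed to both outcomes.

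The Introduction names unnecessary delay of extubation as a harm of a false positive CLT. Under these definitions the extreme form of that harm, never being extubated, lowers the stridor and reintubation proportions. These are the outcomes that the full trial is meant to study.

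The adherence review would not necessarily show such patients. It singles out failure to extubate in control, and it measures intervention adherence by steroids given after a failed CLT.

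**Working it through.** **1. The plan's own figure.** Four patients a month for 10 months is 4 × 10 = 40. With 1:1 allocation that is about 20 per arm. This is a feasibility target with no power calculation behind it.

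**2. How many might be held.** From the Introduction: laryngeal edema (LE) in 4-55% of patients, CLT sensitivity for LE 0.56, specificity 0.92.

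Share failing = 0.56p + 0.08(1 − p), where p is the LE incidence.
- p = 0.04: 0.0224 + 0.0768 = 0.099, or 2.0 of 20.
- p = 0.55: 0.308 + 0.036 = 0.344, or 6.9 of 20.

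These patients fail the test. They are not patients never extubated.

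**3. Effect of one never-extubated patient in 20.** The ceiling is 1/20 = 5 percentage points, which assumes the patient would certainly have had the event. The expected shift uses the chance that a failed CLT indicates LE:
- p = 0.04: 0.0224/0.0992 = 0.226, and 0.226 × 5 = 1.1 points.
- p = 0.55: 0.308/0.344 = 0.895, and 0.895 × 5 = 4.5 points.

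The Introduction says 3.5% (range 0-10.5%) of patients with LE need reintubation. For LE-related reintubation the shift is then 1.1 × 0.035 = 0.04 to 4.5 × 0.035 = 0.16 points, and at most 4.5 × 0.105 = 0.47. Reintubation for other causes is not in this figure.

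**4. Direction of the bias when the CLT strategy has no true effect.** Let u be the share of failed-CLT intervention patients who are never extubated. The protocol does not give u, so every value is an assumption. LE stands in for stridor, and those held are taken as typical of those who fail.

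Counted over all randomized patients, the intervention proportion is p − u × sensitivity × p, so the risk ratio (RR) is 1 − u × sensitivity. For reintubation the Introduction gives sensitivity 0.63. If never-extubated patients are excluded, the RR is (1 − 0.56u)/(1 − uf), where f is the share failing. At p = 0.20, f = 0.112 + 0.064 = 0.176.

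| u | Stridor RR, all randomized | Reintubation RR, all randomized | Stridor RR, extubated only (p = 0.20) |
|---|---|---|---|
| 10% | 0.94 | 0.94 | 0.96 |
| 25% | 0.86 | 0.84 | 0.90 |
| 50% | 0.72 | 0.69 | 0.79 |

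Both ways of counting fall below 1. Exclusion does not cure the problem, because the patients removed are at higher risk than average and their control counterparts stay in.

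**5. Chance that this alone reaches p < 0.05.** With 20 per arm, incidence 10-20% and u from 10% to 50%, it is about 3-7%. With an assumed 500 per arm and 20% incidence it is 6.5% (u = 10%), 20.5% (25%) and 65.1% (50%). The 500 is illustrative only; the protocol gives no size for the full trial.

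**The case against.** **It could be left to the analysis plan.** How to count patients who never become at risk is often settled there, and no sentence in the protocol scores them as event-free. This stands in part: the scoring is an inference. But the protocol itself fixes the time origin, the difference between arms and the intention-to-treat proportions. Together these give a non-event unless another rule is written.

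**The definitions are sound.** Postextubation events can only be timed from extubation. This stands, and the definitions should stay.

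**Few patients are affected.** Every patient has an extubation order, high-risk and palliative patients are excluded, and the only delay described is 24 hours. This stands as an argument that the number is small. It does not make the number zero.

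**It is partly covered already.** Ventilation days run from randomization, and mortality is recorded. Held patients would show there, though death shortens ventilation days, and neither measure corrects the airway comparison.

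**Stronger readings that a reader might infer.**
- That delay itself biases these outcomes. It does not: a patient delayed and then extubated keeps the full 48-hour and 72-hour windows.
- That 2-7 of 20 patients escape risk. That is the share failing the test, and its upper end uses the 55% LE figure although this trial excludes patients at high risk of LE.
- That the pilot's arm estimates will be carried into the full trial. The Discussion says only that the results will help inform its design and conduct.

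**Conclusion.** The point holds in a limited form. Exposure to stridor and reintubation is conditional on the CLT result in one arm only, and a patient never extubated counts in the intervention's favour under intention to treat. Exclusion leaves a bias in the same direction.

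The size is unknown because the documents give no rate of never being extubated. Per such patient in 20, the shift is at most 5 points, with about 1.1-4.5 expected for LE and 0.04-0.16 for LE-related reintubation at the 3.5% figure. These values rest on the pooled accuracy figures, on LE standing in for stridor, and on held patients being typical of those who fail the test.

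A reader might infer that the pilot's main result is compromised. The documents do not support that: its primary outcomes are consent, recruitment and adherence, and with 20 per arm this effect alone would rarely reach significance. The issue matters mainly if the same definitions serve the full trial, where a systematic shift does not shrink with sample size.

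**What to change.** - Keep the 48-hour and 72-hour definitions.
- Report stridor and reintubation over all randomized patients, with the number never extubated shown beside them as a separate category by arm.
- Add one secondary outcome counted from randomization in every patient: either time to first extubation with death as a competing event, or being alive and free of invasive ventilation at a fixed day.
- State a convention for patients who left the ICU or hospital before that day. Daily review stops at ICU discharge, and after that only in-hospital mortality is assessed, so ventilation and vital status are not otherwise known for them.

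The cost is a few lines in the outcome and analysis sections and one more reported outcome. The data come mostly from the daily ICU ventilation records and in-hospital mortality already planned. No extubation or steroid rule changes. The pilot would also show how often non-extubation occurs, which the full trial needs to know.

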Endotracheal intubation and mechanical ventilation are lifesaving interventions. However, as with acute interventions, can be associated with serious complications. One such complication is laryngeal edema (LE) that occurs in 4-55% of patients¹⁻⁵. LE is thought to be caused by marked polymorphonuclear infiltration to the traumatized upper airway postintubation⁶. The incidence of LE increases as the duration of intubation accrues, but it can occur as early as the first 24 hours of intubation⁵. LE can result in airway narrowing and increased airflow velocity. It is postulated that narrowing of the lumen by 50% or more may result in postextubation stridor and respiratory distress⁷. As a result, 3.5% (range 0-10.5%) of patients with LE will fail an extubation attempt and require reintubation⁵. For various reasons, reintubation has a significant morbidity and mortality⁸⁻¹³.

Identifying patients with LE can be challenging, the presence of the endotracheal tube (ETT) precludes direct visualization of the upper airway prior to extubation, therefore, clinicians cannot accurately predict airway obstruction before it occurs. A cuff-leak test (CLT) was first described in 1988 as a surrogate for direct visualization and a screening for airway edema prior to extubation¹⁴. This test involves deflating the balloon cuff on an ETT and observing if the patient is able to breathe around it. If air can pass around the ETT, it suggests that the airway is patent and clinicians may proceed with extubation¹⁴. A small leak or complete absence of one, would suggest an airway obstruction.

There are conflicting results on the utility and accuracy of a CLT. To date, two meta-analyses of observational studies examined the diagnostic accuracy of a CLT^{5,15}. One meta-analysis reports

that a failed CLT is insensitive but a specific predictor of LE (pooled sensitivity and specificity 0.56; 95% CI, 0.48-0.63 and 0.92; 95% CI, 0.90-0.93, respectively) and reintubation (pooled sensitivity and specificity for reintubation 0.63; 95% CI, 0.38-0.84 and 0.86; 95% CI, 0.81-0.90, respectively)¹⁵. While the second meta-analysis also states that the failed CLT was associated with postextubation LE, particularly in patients with > 5 days duration of intubation (odds ratio [OR]=2.09; 95% CI, 1.28-2.89), it was not associated with higher odds of reintubation (OR=0.94; 95% CI, 0.32-1.57)⁵.

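### Ventilation duration and ICU stay are compared as raw elapsed days, so death stops the clock as liberation or discharge alive does and an early death scores as a short course

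*Protocol*

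**What the plan says.** Under Clinical Outcomes, item 7 reads "Duration of mechanical ventilation: defined as time on the ventilator after randomization in days" and item 8 reads "ICU length of stay in days". Neither has a clause for patients who die.

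Data collection and follow-up gives the only limit: "Mortality, duration of ventilation, and ICU stay outcomes will be censored at 60 days".

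Analysis of the COMIC Pilot Trial states that "clinical outcomes will be analyzed as means or proportions in each arm" and that "A t-test will be used for continuous outcomes and a statistical significance will be set at alpha=0.05". It adds "We will develop a full statistical analysis plan adherent to the intention to treat principle", so patients who die stay in the comparison.

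ICU and hospital mortality are listed as separate clinical outcomes. The protocol mentions no survivors-only summary, free-days score, worst rank or competing-event method.

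**The concern.** The variable (elapsed days), the summary (arm mean), the test (t-test) and the analysis set (all randomized) are all fixed. Together they give a death the same standing as a recovery at the same time. The 60-day rule does not help. A t-test on means cannot use censored times, so the rule acts only as a cap on long courses and assigns nothing to a death on day 3.

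Fewer days will be read as better, because the Introduction names a prolonged ICU stay as a harm of a false-positive cuff leak test (CLT). Death is also tied to the event under study, since the Introduction says that "reintubation has a significant morbidity and mortality". The two outcomes show the cost of delaying extubation, and fatal extubation failures distort that reading.

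**Working it through.** The protocol states no effect size, SD or death rate for these outcomes, so there is no figure to reproduce. The check is of ordering, direction and rough size.

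**1. Two patients (illustrative).** A is reintubated on day 1 and dies on the ventilator on day 3: about 3 days on both outcomes. B is reintubated on day 1, liberated on day 9 and leaves the ICU alive on day 12: about 9 and 12 days. The stated rule ranks A above B on both.

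**2. One death in a 20-patient arm** (40 patients, 1:1). Shift in the arm mean = (day of death − course replaced)/20.

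- Day 2 in place of an 8-day course: (2 − 8)/20 = −0.30 day
- Day 3 in place of a 10-day course: (3 − 10)/20 = −0.35 day
- Day 3 in place of a 14-day course: (3 − 14)/20 = −0.55 day
- Day 3 in place of a quick success at 0.15 day: (3 − 0.15)/20 = +0.14 day

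The sign depends on what the death replaces.

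**3. Comparison with the delay effect.** The Introduction gives laryngeal oedema in 4 to 55% of patients, with CLT sensitivity 0.56 and specificity 0.92. The fail rate is then 0.04×0.56 + 0.96×0.08 = 0.099 up to 0.55×0.56 + 0.45×0.08 = 0.344. If every failed test led to the 24-hour delay described under Intervention, the arm mean would rise by 0.10 to 0.34 day. One death in place of a long course is of that order. The upper end is generous, because the trial excludes patients at high risk of oedema.

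**4. Arm means for ventilation time.** Assumptions: a successful patient has 0.15 day (midpoint of 0.05 to 0.25); a reintubated survivor has 8 days; a reintubated patient who dies does so at 10 to 60% of that course, on average 0.35×8 = 2.8 days. With reintubation risk r and death risk q after reintubation:

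mean = (1 − r)×0.15 + r×[(1 − q)×8 + q×2.8]

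*Equal r, different q.* Difference = −r×(q₁ − q₂)×5.2.

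| r | q 50% v 25% | q 50% v 10% |
|---|---|---|
| 10% | −0.13 | −0.21 |
| 15% | −0.20 | −0.31 |
| 20% | −0.26 | −0.42 |

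The arm with more deaths looks better.

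*Different r and q.*

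- r 20%, q 50%: 0.8×0.15 + 0.2×(4 + 1.4) = 1.20 days
- r 10%, q 25%: 0.9×0.15 + 0.1×(6 + 0.7) = 0.81 day
- Difference: +0.40 day (from unrounded means), so the arm with more deaths looks worse
- Same comparison with q 25% in both arms: 0.8×0.15 + 0.2×6.7 = 1.46, a difference of +0.66 day

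The higher fatality removes 1.46 − 1.20 = 0.26 day from the visible harm.

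**5. Noise.** With reintubated courses fixed at 8 days, SD = (8 − 0.15)×√[r(1 − r)] = 2.36 at r 10% and 3.14 at r 20%. The SE of the difference is SD×√(2/20) = 0.74 to 0.99 day. The 0.13 to 0.42 day shifts are below one SE.

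ICU stay was not modelled separately.

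**The case against.** A reader might infer that an arm with more fatal extubation failures will always show a shorter mean, so that harm reads as benefit. The documents do not support that. Patients enter with an extubation order (Population), so most will have very short ventilation after randomization, and a fatal failure that replaces a quick success lengthens the mean. The sign reverses only when deaths replace longer non-fatal courses. Nothing in the protocol suggests that knowing the CLT result changes fatality at equal reintubation risk, which is what the shifts in the table assume. This objection stands in full; what survives it is that the harm is understated when the sign does not reverse.

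A second objection is that scoring deaths is ordinary SAP content and an SAP is promised. That would answer a mere gap. Here the protocol has already chosen the variable, the mean and the t-test, so the SAP would have to override stated methods.

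Third, raw days are a legitimate measure of ventilator exposure and resource use, and the protocol nowhere says that these outcomes measure speed of recovery. That is a reason to keep raw days as description. It does not justify resting the between-arm comparison on them.

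Fourth, little in this pilot turns on the result: the primary outcomes are consent, recruitment and adherence, mortality is reported alongside, and few deaths are likely. This stands and limits the weight of the point.

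**Conclusion.** The point holds as a badly fixed comparison of two non-primary outcomes. The stated method ranks an early death on the ventilator or in the ICU above survival after a longer course. It makes an arm look better when deaths replace longer non-fatal courses, and understates the harm when deaths replace quick successful extubations.

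The size cannot be fixed from the protocol. It gives no expected death rate, and its one reintubation figure (3.5%, range 0 to 10.5%) concerns patients with laryngeal oedema. Under the assumed 10 to 20% reintubation and 10 to 50% death after reintubation, the shift is 0.13 to 0.42 day, and it shrinks in proportion to the reintubation risk. That is below one standard error at 20 per arm, so the pilot's own conclusions are unlikely to rest on it. The change should be made chiefly because Feasibility Outcomes presents the clinical outcomes as those of interest for the later RCT, where the same definition could be carried forward.

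**What to change.** Beside the 60-day sentence in Data collection and follow-up, and in the analysis section, state that:

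- Raw ventilator days and ICU days are descriptive, shown overall and separately for survivors and non-survivors.
- For these two outcomes the t-test is replaced by a comparison of time to liberation from ventilation alive and time to ICU discharge alive, with death as a competing event and censoring at day 60. Patients who die stay in the denominator as never liberated or discharged alive. Simply censoring them at death would not do this.
- Liberation is defined so that a reintubated patient is not counted as liberated at the first extubation.

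A rank-based comparison with death as the worst rank is an acceptable alternative. A mean with deaths set to 60 days is less suitable: in the equal-r scenarios it moves the difference by r×(q₁ − q₂)×(60 − 8), that is 0.10×0.25×52 = 1.3 to 0.20×0.40×52 = 4.2 days, and would swamp a delay effect of 0.10 to 0.34 day.

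The cost is a few lines of wording and code. Daily ICU review already gathers mortality, stay and ventilation time. The one downside is that the between-arm summary then combines recovery with survival, so raw days and mortality must be shown beside it.

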If we are unable to locate the SDM for *a priori* consent, then patients may be enrolled using deferred consent until the SDM can be contacted as permitted by local REBs. The consent encounter will occur as soon as possible. If, when found, the SDM response could be permission to continue all trial proceedings, or decline further trial proceedings. In the latter situation, data collected will be used up to that point, unless the SDM requests otherwise. For the patient who has no identifiable family member, or power of attorney to provide consent, we propose to continue study protocols while we attempt (and the ICU team attempts) to locate a SDM and/or the patient recovers. In the event that such a patient subsequently recovers to the extent that an informed consent can be provided, we will ask the patient for their consent.

Deferred consent model is crucial to ensure the proper conduct of the COMIC Trial. To begin with, extubating patients is a daily routine in the ICU, and should not be delayed unless there is a valid reason to do so. Therefore, we will allow a one hour window for the study Research Coordinator (RC) to obtain *a priori* consent whenever possible, but mandating *a priori* consent

will make this study infeasible. Although CLT is commonly performed in the ICU prior to extubation, there is no clear evidence that this practice benefit patients⁵, in fact performing a CLT routinely could result in harm in some patients by delaying extubation unnecessarily and exposing them to high dose corticosteroids. The results of this trial will inform practice about an intervention that is being used for decades with lack of high quality evidence. We have successfully used deferred consent model in recent a RCT²². Several other large, multicenter, international RCTs have successfully used deferred consent model in acute settings²², and it would not have been possible to inform practice and conduct those trials without a deferred consent model.

Randomization and allocation concealment

The study RC will use the web-based system RANDOMIZE.NET (<http://www.randomize.net/>) to randomize eligible patients in a 1:1 allocation using undisclosed variable block sizes. Randomization will be stratified by: a) ETT size into three strata (6, 7, 8 mm ETTs), and b) duration of mechanical ventilation prior to randomization into two strata (>7 days and \leq 7days).

Intervention

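### Randomization is stratified, but the named t-test ignores the strata and the Mantel-Haenszel strata are not stated; if the strata are prognostic, the arm comparisons are conservative

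*Protocol*

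**What the plan says.** In the protocol, the section on randomization and allocation concealment states "Randomization will be stratified by: a) ETT size into three strata (6, 7, 8 mm ETTs" and, as the second factor, "duration of mechanical ventilation prior to randomization into two strata", cut at 7 days. That makes 3 × 2 = 6 cells. The web system will "randomize eligible patients in a 1:1 allocation using undisclosed variable block sizes".

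The section on analysis of the pilot trial then names the comparisons. For continuous outcomes: "A t-test will be used for continuous outcomes and a statistical significance will be set at alpha=0.05". For proportions it names a Mantel-Haenszel chi-square "test or Fisher exact test". No stratum or covariate is attached to any of these, and there is no rule for choosing between the two tests for proportions. The same section promises a full statistical analysis plan.

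The continuous clinical outcomes in the list are ventilation time after randomization and ICU length of stay. The primary outcomes are feasibility measures.

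**The concern.** Stratified blocks make the arms more alike on the stratification factors than simple randomization would. An analysis that leaves those factors out still counts the between-stratum variation as noise, although the design has largely removed it from the arm difference. Where the factors are prognostic, the reported standard error is too large and the test rejects less often than its nominal level.

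A two-sample t-test has no place for strata, so for ventilation time and ICU stay the mismatch lies in the named method itself. For proportions the position is softer: Mantel-Haenszel can carry strata, but the protocol does not say that it will or which ones.

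At stake are the power of the planned tests on the clinical outcomes, the width of any between-arm interval built from the t-test, and whether the analysis rehearsed for the large trial matches its randomization.

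**Working it through.** **Inputs from the protocol.** Two factors with 3 and 2 levels; 1:1 allocation in variable blocks; alpha 0.05 (taken as two-sided, which the protocol does not state). Sample size: "We anticipate that 10 months will be required to recruit 40 patients", and recruitment "conventionally expressed as four patients per month over the duration of the trial". 4 × 10 = 40, so the figure reproduces. That is about 20 per arm and 40/6 ≈ 6.7 per cell. There is no power, standard deviation or event rate to check.

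**Assumptions, not in the protocol.** The share R² of outcome variance explained by the strata (0 to 0.5); stratum shares (ETT 15/50/35%, duration 65/35%); a normal outcome; block sizes of 2/4/6 or 4/6; event rates of 5% to 20%.

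**Continuous outcomes, formula.** The t-test has 40 − 2 = 38 degrees of freedom. Main effects for the strata use (3 − 1) + (2 − 1) = 3, leaving 35. With balanced arms, adjusted width divided by unadjusted width is

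√(1 − R²) × t(0.975; 35) / t(0.975; 38) = √(1 − R²) × 1.003.

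**Simulation.** 4,000 trials per setting, N = 40, blocks within the 6 cells. Where two values are shown they are for the two block schemes. Excess width is 1/(simulated ratio) − 1.

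| R² | Ratio, formula | Ratio, simulated | t-test interval too wide by | Coverage of t-test 95% interval |
|---|---|---|---|---|
| 0 | 1.003 | 1.011–1.012 | none; adjustment about 1% wider | 94.6–95.2% |
| 0.05 | 0.977 | 0.985 | 1.5% | 95.5–95.6% |
| 0.10 | 0.951 | 0.958 | 4% | 95.1–96.3% |
| 0.20 | 0.897 | 0.902–0.903 | 11% | 97.0–97.8% |
| 0.30 | 0.839 | 0.842–0.843 | 19% | 97.0–97.3% |

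Adjusted coverage stayed between 94.1% and 96.0%. The simulated ratios lie slightly nearer 1 than the formula because incomplete blocks leave the arms not exactly balanced.

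The spread of the estimate itself hardly changes. At R² = 0.20 its standard deviation is 0.285 unadjusted and 0.282 adjusted (2/4/6 blocks). The loss is mainly an overstated standard error.

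**Proportions with no true effect.** Rejection rates at nominal 5%; the first value is with non-prognostic strata, the second with a duration odds ratio of 3.

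| Event rate | Fisher | Mantel-Haenszel over 6 cells | Not computable (Mantel-Haenszel) |
|---|---|---|---|
| 5% | 0.3%, 0.4% | 1.1%, 1.6% | 13.5%, 10.1% |
| 10% | 1.5%, 1.8% | 2.9%, 3.8% | 1.7%, 1.2% |
| 20% | 2.7%, 2.6% | 4.9%, 5.2% | below 0.1% |

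Fisher is about equally conservative whether or not the strata matter, so its conservatism comes mainly from discreteness. Most of the non-computable cases are trials with no event at all: 0.95^40 = 12.9% at a 5% rate and 0.90^40 = 1.5% at 10%.

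**The case against.** The strongest reply is that adjustment for stratification factors is commonly settled in the statistical analysis plan, which the protocol promises. That would answer a protocol that was silent. This one names a t-test, and a plan that follows it inherits the mismatch. For proportions the reply has more force: what is left there is an unstated choice of strata.

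Other objections stand and limit the point:

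- A reader might infer that the loss is certain. It is not. The Introduction links longer intubation to more laryngeal edema, and the Discussion lists a large tube among guideline risk features. Both statements are qualitative and concern the airway. Nothing in the protocol shows that either factor predicts ventilation time or ICU stay, and no reason is given for choosing the strata.
- A reader might infer that the trial's planned confidence intervals are too wide. The only interval named is for the overall consent proportion, which is not analysed by group. The planned item affected is the test; a between-arm interval would be derived from it.
- A reader might blame Fisher's low rejection rate on ignored strata, or conclude that the effect estimates lose much precision. The working supports neither.
- The feasibility outcomes are rates and proportions judged against fixed targets, so those judgements do not depend on the t-test.

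**Conclusion.** The point holds in limited form. The protocol randomizes within strata and names a method for ventilation time and ICU stay that cannot use them; for proportions it leaves the Mantel-Haenszel strata open. If the strata are prognostic, the t-test is conservative, and an interval derived from it is about 1.5% to 4% too wide at R² of 0.05 to 0.10 and about 11% to 19% too wide at 0.20 to 0.30. If they are not, nothing is lost.

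The sizes rest on an assumed R², assumed stratum shares and a normal outcome. The direction (too cautious, never too liberal) follows from the design once the strata are prognostic. In a 40-patient pilot with feasibility as its primary aim, this is a low-cost improvement and does not threaten the trial's conclusions.

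**What to change.** For ventilation time and ICU stay, replace the t-test with a linear model containing arm, ETT size and prior-ventilation group as main effects, and report the adjusted arm difference with its 95% interval.

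For proportions, state that the Mantel-Haenszel analysis is stratified by the two prior-ventilation groups (up to 7 days, more than 7 days), fixed in advance, with Fisher's exact test kept as a check when events are sparse. Whether ETT size enters should not depend on which cells turn out empty. If its categories need collapsing, fix the rule before unblinding.

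The cost is a change of wording, 3 of 38 degrees of freedom, and about 1% in interval width if the strata are not prognostic. The linear model shares the t-test's limits for durations censored at 60 days; this change does not address that.
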